**5.4.5 COVID-19 related analyses**

Subjects affected by the COVID-19 pandemic will be listed with the affected visits, the visit adherence and drug dispensation method.

**5.4.6 Pregnancies**

Please refer to SAP, version 4.1.

**5.4.7 Vital Signs**

Not applicable.

**5.4.8 Clinical Laboratory Tests**

Descriptive statistics (mean, standard deviation median, minimum and maximum) will be provided for the laboratory parameters serum creatinine and estimated glomerular filtration rate (eGFR) at the LTOLE initiation visit.

**6. Definitions**

Final LTOLE Follow-up Visit	Final visit at the end of the LTOLE follow-up of the COMPASS trial
Last LTOLE Follow-up Date	
If consent was not withdrawn:  Last LTOLE Follow-up Date                      = first of
 
 
○ date of death (if applicable)
 
○ maximum date of completed Final LTOLE Follow-up visit and last study drug intake, if Final LTOLE Follow-up Visit is completed
 
○ max (dates of visits completed during LTOLE, event dates during LTOLE).
 
 
If consent was withdrawn:  Last LTOLE Follow-up Date                      = first of
 
 
• max (date of death, date of withdrawal, date of confirmed alive)
 
○ maximum date of completed Final LTOLE Follow-up visit (if applicable) and last study drug intake
 

	•
Last rivaroxaban/aspirin Follow-up Date	As defined for CDB1
Last pantoprazole/placebo Follow-up Date	As defined for CDB2
Last Follow-up Date	
If subject is in LTOLE ITT set:  Last Follow-up Date = Last LTOLE Follow-up Date
 
Else If subject is in pantoprazole ITT set:  Last Follow-up Date = Last pantoprazole/placebo Follow-up Date
 
Else If subject is not randomized to pantoprazole/placebo:  Last Follow-up Date = Last rivaroxaban/aspirin Follow-up Date

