## Statistical Analysis Plan

	
 
• max (dates of visits completed, event dates).
 
 
If consent was withdrawn:
 
Last pantoprazole/placebo Follow-up Date
 
= first of
 
 
• max (date of death, date of withdrawal, date of confirmed alive)
 
• date of completed Final pantoprazole/placebo Follow-up visit (if applicable).
 

Last Follow-up Date	
If subject is in pantoprazole ITT set:
 
Last Follow-up Date = Last pantoprazole/placebo Follow-up Date
 
If subject is not randomized to pantoprazole/placebo:
 
Last Follow-up Date = Last rivaroxaban/aspirin Follow-up Date

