## 4.2 Data scopes and censoring rules

The following data scopes will be considered:

- LTOLE follow-up
  - From date of LTOLE initiation visit to last LTOLE follow-up date
- LTOLE treatment emergent
  - From LTOLE initiation visit until last date of drug intake of LTOLE study medication + 2 days
- COMPASS follow-up
  - From randomization until last Follow-up date as defined in section 6.

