### **5.4.4 Death**

Deaths will be summarized by cardiovascular cause and non-cardiovascular cause

- from randomization to last trial contact (in ITT set)
- from LTOLE initiation to last trial contact (in LTOLE ITT set).

For these data scopes the number of subjects with an event, the crude incidences and the incidence rates will be presented.

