### **7. Document History and Changes in the Planned Statistical Analysis**

Version 2 implements analyses with respect to COVID-19 pandemic, updated definition of Last LTOLE Follow-up date due to reported number of patients that reported to take study drug after final LTOLE visit and minor changes for the analyses of prior and concomitant medication.

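### LTOLE SAP, Last LTOLE Follow-up Date with consent withdrawn: read literally, a subject without a final visit has follow-up ended at last drug intake

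*SAP*

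**What the plan says.** The LTOLE SAP, section 6, defines Last LTOLE Follow-up Date in two branches. Each takes the first of a list of dates.

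- **Consent withdrawn.** Item (a) is the latest of the death, withdrawal and confirmed-alive dates. Item (b) is the "maximum date of completed Final LTOLE Follow-up visit (if applicable) and last study drug intake".
- **Consent not withdrawn.** The matching item is the "maximum date of completed Final LTOLE Follow-up visit and last study drug intake, if Final LTOLE Follow-up Visit is completed". Here the closing condition governs the whole item.

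Section 4.2 builds two scopes that matter here. LTOLE follow-up runs "From date of LTOLE initiation visit to last LTOLE follow-up date". The treatment-emergent scope runs "From LTOLE initiation visit until last date of drug intake of LTOLE study medication + 2 days". A third scope, COMPASS follow-up, ends at Last Follow-up Date, which section 6 sets equal to Last LTOLE Follow-up Date for every subject in the LTOLE ITT set.

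Section 5.4.4 summarises deaths on a different window, "from LTOLE initiation to last trial contact (in LTOLE ITT set").

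The earlier PPI SAP, section 6, has the same two-item form for withdrawn subjects: "max (date of death, date of withdrawal, date of confirmed alive"), and "date of completed Final pantoprazole/placebo Follow-up visit (if applicable"). It has no drug-intake term.

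Section 7 of the LTOLE SAP gives the reason for the version 2 change: "updated definition of Last LTOLE Follow-up date due to reported number of patients that reported to take study drug after final LTOLE visit".

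**The concern.** In the withdrawn branch the words *if applicable* follow the visit, not the whole item. With no final visit, item (b) does not drop out; it shrinks to last study drug intake. Because the rule takes the first of (a) and (b), follow-up then ends at last intake whenever drug stopped before withdrawal. Item (a), which exists to use withdrawal and later vital-status dates, has no effect for these subjects.

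A scope meant to follow the LTOLE ITT set regardless of treatment would become an on-treatment scope for exactly the subjects who stopped drug and later withdrew. In crude incidences the subject stays in the denominator while later observed events are removed, so those figures can only fall or stay the same. In incidence rates both events and person-time are removed, so the direction is not fixed.

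**Working it through.** The documents give no figure on this point, so there is none to reproduce. The check applies the rule as worded and compares it with the rule in which item (b) counts only when the final visit was completed.

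Formulas:

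- Literal: end = min{ max(death, withdrawal, confirmed alive), max(final visit if any, last intake) }.
- Conditional: the same if a final visit was completed; otherwise end = max(death, withdrawal, confirmed alive).
- Treatment-emergent end = last intake + 2 days (section 4.2).

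The day numbers are illustrative assumptions, counted from LTOLE initiation.

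| Case | Literal end | Conditional end | Days lost | Treatment-emergent end |
|---|---|---|---|---|
| Stop 200, event 300, withdrawal 400, no final visit | min(400, 200) = 200 | 400 | 200 | 202 |
| Stop 200, withdrawal 400, confirmed alive 700, no final visit | min(700, 200) = 200 | 700 | 500 | 202 |
| Stop 200, withdrawal 400, death 600, no final visit | min(600, 200) = 200 | 600 | 400 | 202 |
| Stop and withdrawal both 400, nothing recorded later | min(400, 400) = 400 | 400 | 0 | 402 |
| Stop 200, withdrawal 400, alive 800, final visit 800 | min(800, 800) = 800 | 800 | 0 | 202 |

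What follows:

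1. In the first case the day-300 event is lost along with 200 observed days. In the third, the death falls outside the follow-up scopes but stays in section 5.4.4, which runs to last trial contact.
2. In the first three cases the follow-up scope (day 200) ends before the treatment-emergent scope (day 202). An event on day 201 would count in the on-treatment safety table but not in the follow-up table.
3. The two rules agree when a final visit exists. They also agree when drug stop and withdrawal coincide and no vital status is recorded later.

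Tables affected: the efficacy counts and rates of section 5.2.2, the bleeding tables of section 5.4.1 for the LTOLE ITT set, and the whole-study counts and crude incidences in the COMPASS follow-up scope. Section 5.2.2 names an LTOLE ITT data scope that section 4.2 does not define; I take it to be the LTOLE follow-up scope.

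Three comparisons within the documents point to a drafting slip: the not-withdrawn branch conditions the whole item, the PPI rule has no drug-intake term, and the version 2 change responded to drug taken after the final visit. That change was meant to lengthen follow-up; for these subjects the literal wording shortens it.

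**The case against.** The best reply is that *if applicable* can govern the whole item. In the PPI SAP the same words make the item drop out when there is no visit. The version 2 rationale also presupposes a completed final visit. On that reading item (a) alone applies and nothing is lost. This stands as a possible reading. The position of the words and the contrast with the other branch favour the literal one, but two programmers could derive different dates, which is itself a reason to settle the text. The layout of that table cell is untidy, possibly only from text extraction, so nothing here rests on it.

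Stronger claims that a reader might infer are not supported:

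- *Deaths between stopping drug and withdrawal are deleted.* A subject who withdraws consent is alive on that date. Only deaths recorded after withdrawal can be affected.
- *Those deaths vanish from the report.* Section 5.4.4 keeps them. The risk is disagreement between the mortality figures of section 5.2.2 and that summary.
- *A known share of person-time is lost.* The share would be withdrawal share × gap ÷ mean follow-up. With assumed values it could be 0.03 × 6/30 = 0.6% or 0.10 × 18/30 = 6%, and it falls to zero when the gap is zero. The documents give none of these inputs.
- *Trial conclusions are biased.* Section 5.2 describes LTOLE as single-arm with no testing of treatment effects. The adverse event tables and the safety-set bleeding tables end at last intake + 2 days in any case.

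**Conclusion.** The point holds as a wording defect with a definite consequence on the literal reading. It needs consent withdrawn, no final LTOLE visit, and drug stopped before withdrawal. Observed time and non-fatal events from last intake to withdrawal, and deaths or confirmed-alive time recorded later, then leave the LTOLE and COMPASS follow-up scopes. Per subject the loss is the whole interval from last intake to the date that item (a) would have given: 200 to 500 days in the illustrative cases. The total effect cannot be derived from the documents. It touches descriptive counts, crude incidences and rates only, but these make up the LTOLE efficacy output, so the correction is worth making.

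**What to change.** In the consent-withdrawn branch of Last LTOLE Follow-up Date, apply the later of final-visit date and last drug intake only if the final LTOLE visit was completed, matching the not-withdrawn branch. Without that visit, use the latest of the death, withdrawal and confirmed-alive dates alone. This keeps the extension that version 2 intended for drug taken after the final visit. The cost is one clause in section 6 and one line in the derivation, with no new data. Any table already produced on the literal rule would need to be rerun.

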**6.1 Arrangement of LTOLE and non-LTOLE events**

In the LTOLE part of the study there is no adjudication of efficacy events, contrary to the antithrombotic as well the pantoprazole/placebo part of the study. For an arrangement for the whole study the following definitions hold:

- For event types not adjudicated at any time of the study: count all events as reported
- For events adjudicated at any time of the study:
  - Unrefuted events are all events confirmed in an adjudication plus the events that did not undergo adjudication
  - Investigator reported events are all events reported by the investigators regardless of any result of the adjudication process.

For the LTOLE part of the study the event CRF pages were simplified. The event “Bleeding leading to hospitalization” was not queried on the CRF page in the LTOLE event form. Thus all hospitalization with primary reason for admission “bleeding” will be counted for these events.

In the LTOLE event CRF the reasons for hospitalization are simplified and especially the other diagnoses is not divided into CV and non-CV reasons. Thus the event “Hospitalization for CV reasons” for the whole study is the combination of Hospitalizations for CV reasons as defined for CDB1 and CDB2 for the antithrombotic and pantoprazole/placebo part of the study and the events with reasons defined in section 5.2.1 as “cardiovascular reasons” for events during the LTOLE part of the study.

The event “Severe Limb Ischemia” was reported differently in the main part of the study and the LTOLE part. However, for the data scopes from randomization onwards the events of the antithrombotic and pantoprazole/placebo part will be combined with the events collected in LTOLE.

### **7. Document History and Changes in the Planned Statistical Analysis**

Version 2 implements analyses with respect to COVID-19 pandemic, updated definition of Last LTOLE Follow-up date due to reported number of patients that reported to take study drug after final LTOLE visit and minor changes for the analyses of prior and concomitant medication.

